### **5.4 Stratification**

No stratification is to be performed.

### **5.5 Concomitant Medications/Vaccinations (allowed & prohibited)**

Medications or vaccinations specifically prohibited in the exclusion criteria are not allowed during the ongoing trial. If there is a clinical indication for one of these or other medications or

vaccinations specifically prohibited during the trial, discontinuation from trial therapy or vaccination may be required. The investigator should discuss any questions regarding this with the Principal Investigator. The final decision on any supportive therapy or vaccination rests with the treating investigator and/or the subject's primary physician.

### 5.5.1 Acceptable Concomitant Medications

All treatments that the investigator considers necessary for a subject's welfare may be administered at the discretion of the investigator in keeping with the community standards of medical care. All concomitant medication will be recorded on the case report form (CRF) including all prescription, over the counter (OTC), herbal supplements, and IV medications and fluids. If changes occur during the trial period, documentation of drug dosage, frequency, route, and date may also be included on the CRF.

All concomitant medications received within 28 days before the first dose of trial treatment and 30 days after the last dose of trial treatment should be recorded. Concomitant medications administered after 30 days after the last dose of trial treatment should be recorded for SAEs and ECIs as defined in Section 7.2.

### 5.5.2 Prohibited Concomitant Medications

Subjects are prohibited from receiving the following therapies during the Screening and Treatment Phase of this trial:

- Antineoplastic systemic chemotherapy or biological therapy
- Immunotherapy not specified in this protocol
- Investigational agents other than pembrolizumab
- Radiation therapy outside of that prescribed per protocol
- Live vaccines within 30 days prior to the first dose of trial treatment and while participating in the trial. Examples of live vaccines include, but are not limited to, the following: measles, mumps, rubella, varicella/zoster, yellow fever, rabies, BCG, and typhoid vaccine.
- Systemic glucocorticoids for any purpose other than to modulate symptoms from an event of clinical interest of suspected immunologic etiology. The use of physiologic doses of corticosteroids may be approved after consultation with the Principal Investigator.

Subjects who, in the assessment by the investigator, require the use of any of the aforementioned treatments for clinical management should be removed from the trial. Subjects may receive other medications that the investigator deems to be medically necessary.

The Exclusion Criteria describes other medications which are prohibited in this trial. There are

no prohibited therapies during the Post-Treatment Follow-up Phase.

## **5.6 *Rescue Medications & Supportive Care***

### 5.6.1 Supportive Care Guidelines

Subjects should receive appropriate supportive care measures as deemed necessary by the treating investigator. Suggested supportive care measures for the management of adverse events with potential immunologic etiology are outlined below. Where appropriate, these guidelines include the use of oral or intravenous treatment with corticosteroids as well as additional anti-inflammatory agents if symptoms do not improve with administration of corticosteroids. Note that several courses of steroid tapering may be necessary as symptoms may worsen when the steroid dose is decreased. For each disorder, attempts should be made to rule out other causes such as metastatic disease or bacterial or viral infection, which might require additional supportive care. The treatment guidelines are intended to be applied when the investigator determines the events to be related to pembrolizumab.

Note: if after the evaluation the event is determined not to be related, the investigator does not need to follow the treatment guidance (as outlined below). Refer to Section 5.2.1 for dose modification.

It may be necessary to perform conditional procedures such as bronchoscopy, endoscopy, or skin photography as part of evaluation of the event.

### 5.6.2 Pneumonitis:

5.6.2.1 For **Grade 2 events**, treat with systemic corticosteroids. When symptoms improve to Grade 1 or less, steroid taper should be started and continued over no less than 4 weeks.

5.6.2.2 For **Grade 3-4 events**, immediately treat with intravenous steroids. Administer additional anti-inflammatory measures, as needed.

**5.6.2.3** Add prophylactic antibiotics for opportunistic infections in the case of prolonged steroid administration.

### 5.6.3 Diarrhea/Colitis:

Subjects should be carefully monitored for signs and symptoms of enterocolitis (such as diarrhea, abdominal pain, blood or mucus in stool, with or without fever) and of bowel perforation (such as peritoneal signs and ileus).

5.6.3.1 All subjects who experience diarrhea/colitis should be advised to drink liberal quantities of clear fluids. If sufficient oral fluid intake is not feasible, fluid and electrolytes should be substituted via IV infusion. For Grade 2 or higher diarrhea, consider

GI consultation and endoscopy to confirm or rule out colitis.

5.6.3.2 For **Grade 2 diarrhea/colitis**, administer oral corticosteroids.

5.6.3.3 For **Grade 3 or 4 diarrhea/colitis**, treat with intravenous steroids followed by high dose oral steroids.

5.6.3.4 When symptoms improve to Grade 1 or less, steroid taper should be started and continued over no less than 4 weeks.

#### 5.6.4 Type 1 diabetes mellitus\*

\*(if new onset, including diabetic ketoacidosis [DKA]) or  $\geq$  Grade 3 Hyperglycemia, if associated with ketosis (ketonuria) or metabolic acidosis (DKA)

##### 5.6.4.1 For **T1DM** or **Grade 3-4** Hyperglycemia

5.6.4.1.1 Insulin replacement therapy is recommended for Type I diabetes mellitus and for Grade 3-4 hyperglycemia associated with metabolic acidosis or ketonuria.

5.6.4.1.2 Evaluate patients with serum glucose and a metabolic panel, urine ketones, glycosylated hemoglobin, and C-peptide.

#### 5.6.5 Hypophysitis:

5.6.5.1 For **Grade 2** events, treat with corticosteroids. When symptoms improve to Grade 1 or less, steroid taper should be started and continued over no less than 4 weeks. Replacement of appropriate hormones may be required as the steroid dose is tapered.

5.6.5.2 For **Grade 3-4** events, treat with an initial dose of IV corticosteroids followed by oral corticosteroids. When symptoms improve to Grade 1 or less, steroid taper should be started and continued over no less than 4 weeks. Replacement of appropriate hormones may be required as the steroid dose is tapered.

#### 5.6.6 Hyperthyroidism or Hypothyroidism:

Thyroid disorders can occur at any time during treatment. Monitor patients for changes in thyroid function (at the start of treatment, periodically during treatment, and as indicated based on clinical evaluation) and for clinical signs and symptoms of thyroid disorders.

##### 5.6.6.1 **Grade 2** hyperthyroidism events (and **Grade 2-4** hypothyroidism):

5.6.6.1.1 In hyperthyroidism, non-selective beta-blockers (e.g. propranolol) are suggested as initial therapy.

5.6.6.1.2 In hypothyroidism, thyroid hormone replacement therapy, with levothyroxine or liothyronine, is indicated per standard of care.

##### 5.6.6.2 **Grade 3-4** hyperthyroidism

5.6.6.2.1 Treat with an initial dose of IV corticosteroid followed by oral corticosteroids. When symptoms improve to Grade 1 or less, steroid taper

should be started and continued over no less than 4 weeks.

Replacement of appropriate hormones may be required as the

steroid dose is tapered.

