##### 5.2.1.1 Dose Modification (Escalation/Titration/Other)

Adverse events (both non-serious and serious) associated with pembrolizumab exposure, including coadministration with additional compounds, may represent an immunologic etiology. These adverse events may occur shortly after the first dose or several months after the last dose of pembrolizumab/combination and may affect more than one body system simultaneously. Pembrolizumab/combination treatment must be withheld for drug-related toxicities and severe or life-threatening AEs as per Table 3 below. See Section 5.6 for supportive care guidelines, including use of corticosteroids.

If a patient continues to experience toxicity, or if dosing with study drug is interrupted for > 14 consecutive days due to toxicity, treatment should be discontinued unless otherwise agreed between the investigators before reintroduction of study drug.

The following dose modification rules will be used with respect to potential toxicity. Toxicity will be assessed according to the NCI Common Terminology Criteria for Adverse Events [Version 4.0 \(CTCAE v4.0\)](#).

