## General instructions:

1. Severe and life-threatening irAEs should be treated with IV corticosteroids followed by oral steroids. Other immunosuppressive treatment should begin if irAEs are not controlled by corticosteroids.
2. Study intervention must be permanently discontinued if the irAE does not resolve or the corticosteroid dose is not  $\leq$ 10 mg/day within 12 weeks of the last study intervention treatment.
3. The corticosteroid taper should begin when the irAE is  $\leq$  Grade 1 and continue at least 4 weeks.
4. If study intervention has been withheld, study intervention may resume after the irAE decreased to  $\leq$  Grade 1 after corticosteroid taper.

irAEs	Toxicity Grade (CTCAE v5.0)	Action with pembrolizumab	Corticosteroid and/or other therapies	Monitor and Follow-up
Pneumonitis	Grade 2	Withhold	
 
• Administer corticosteroids (initial dose of 1 to 2 mg/kg prednisone or equivalent) followed by taper
 
• Add prophylactic antibiotics for opportunistic infections
 
	
 
• Monitor participants for signs and symptoms of pneumonitis
 
• Evaluate participants with suspected pneumonitis with radiographic imaging and initiate corticosteroid treatment
 

	Recurrent Grade 2, Grade 3 or 4	Permanently discontinue		
Diarrhea/Colitis	Grade 2 or 3	Withhold	
 
• Administer corticosteroids (initial dose of 1 to 2 mg/kg prednisone or equivalent) followed by taper
 
	
 
• Monitor participants for signs and symptoms of enterocolitis (i.e., diarrhea, abdominal pain, blood or mucus in stool with or without fever) and of bowel perforation (i.e., peritoneal signs and ileus)
 
• Participants with <math>\geq</math>Grade 2 diarrhea suspecting colitis should consider GI consultation and performing endoscopy to rule out colitis
 
• Participants with diarrhea/colitis should be advised to drink liberal quantities of clear fluids. If sufficient oral fluid intake is not feasible, fluid and electrolytes should be substituted via IV infusion
 

	Recurrent Grade 3 or Grade 4	Permanently discontinue		

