AST or ALT Elevation or Increased Bilirubin	Grade 2 a	Withhold	
 
• Administer corticosteroids (initial dose of 0.5 to 1 mg/kg prednisone or
 
	
 
• Monitor with liver function tests (consider weekly or more frequently until liver enzyme
 

			equivalent) followed by taper	value returned to baseline or is stable)
	Grade 3 b or 4 c	Permanently discontinue	
 
Administer corticosteroids (initial dose of 1 to 2 mg/kg prednisone or equivalent) followed by taper
 
	
T1DM or Hyperglycemia	New onset T1DM or Grade 3 or 4 hyperglycemia associated with evidence of $\beta$ -cell failure	Withhold d	
 
Initiate insulin replacement therapy for participants with T1DM
 
Administer antihyperglycemic in participants with hyperglycemia
 
	
 
Monitor participants for hyperglycemia or other signs and symptoms of diabetes
 

Hypophysitis	Grade 2	Withhold	
 
Administer corticosteroids and initiate hormonal replacements as clinically indicated
 
	
 
Monitor for signs and symptoms of hypophysitis (including hypopituitarism and adrenal insufficiency)
 

	Grade 3 or 4	Withhold or permanently discontinue d		
Hyperthyroidism	Grade 2	Continue	
 
Treat with nonselective beta-blockers (e.g., propranolol) or thionamides as appropriate
 
	
 
Monitor for signs and symptoms of thyroid disorders.
 

	Grade 3 or 4	Withhold or permanently discontinue 		
Hypothyroidism	Grade 2-4	Continue	
 
Initiate thyroid replacement hormones (e.g., levothyroxine or liothyroinine) per standard of care
 
	
 
Monitor for signs and symptoms of thyroid disorders.
 

Nephritis: grading according to increased creatinine or acute kidney injury	Grade 2	Withhold	
 
Administer corticosteroids (prednisone 1 to 2 mg/kg or equivalent) followed by taper.
 
	
 
Monitor changes of renal function
 

	Grade 3 or 4	Permanently discontinue		

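### Grade 3-4 hyperthyroidism: the Table 3 row names beta-blockers or thionamides, while section 5.6.6.2 and Table 3's own general instructions call for corticosteroids, and nothing says which governs

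*Combined protocol and SAP*

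**What the plan says.** Three places in the protocol bear on therapy for Grade 3-4 hyperthyroidism.

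- **Section 5.6.6.2** (supportive care): "Treat with an initial dose of IV corticosteroid followed by oral corticosteroids". Once symptoms improve to Grade 1 or less, a taper "should be started and continued over no less than 4 weeks".
- **Table 3 in section 5.2.1.1, general instructions 1 and 3**: "Severe and life-threatening irAEs should be treated with IV corticosteroids followed by oral steroids". The taper is to begin at Grade 1 or below "and continue at least 4 weeks".
- **Table 3, hyperthyroidism row, therapy column**: "Treat with nonselective beta-blockers (e.g., propranolol) or thionamides as appropriate". No corticosteroid appears in the row. Its Grade 3 or 4 line carries a dosing action only.

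The two sections point at each other. Section 5.2.1.1 says "See Section 5.6 for supportive care guidelines, including use of corticosteroids". Section 5.6.1 describes its measures as suggestions and sends the reader back to section 5.2.1 for dose modification.

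For pneumonitis, the Table 3 row lists prophylactic antibiotics alongside corticosteroids with no condition. Section 5.6.2.3 adds them "in the case of prolonged steroid administration".

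**The concern.** A clinician who looks up hyperthyroidism in Table 3 and acts on the row gets a different instruction from one who reads the notes at the head of the same table, or who turns to section 5.6.6.2. The event is one for which the protocol requires pembrolizumab to be withheld or stopped, so this is the moment when staff will consult these pages. Two patients with the same event at the same grade could be managed differently, both within the protocol. A monitor would have no basis for calling either course a deviation.

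What is at stake is consistent care of patients with a serious immune-related event.

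**Working it through.** No arithmetic decides this point. The check is a comparison of texts.

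**Step 1: do the general instructions reach Grade 3-4?** Instruction 1 speaks of severe and life-threatening events. The grading scale in section 6.3.2 describes Grade 3 as severe and Grade 4 as life-threatening. So instruction 1 covers the grades that section 5.6.6.2 addresses.

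**Step 2: set the instructions side by side for Grade 3-4 hyperthyroidism.**

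| Source | Therapy named | Taper |
|---|---|---|
| Section 5.6.6.2 | IV, then oral corticosteroids | at least 4 weeks |
| Table 3, general instructions 1 and 3 | IV, then oral corticosteroids | at least 4 weeks |
| Table 3, hyperthyroidism row | beta-blockers or thionamides | none given |

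The first two agree. The row stands alone.

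**Step 3: does the row's therapy cell cover Grade 3-4?** In the text available, the entry sits on the Grade 2 line. The table's habits suggest that it spans the row:

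- Where therapy differs by grade, as in the AST/ALT/bilirubin row, the table prints a second therapy entry on the Grade 3-4 line.
- Where it does not differ, as for pneumonitis, diarrhea/colitis and nephritis, one entry is printed on the first grade line. If those entries did not span, Grade 3-4 pneumonitis and nephritis would have no therapy in their rows.

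The hyperthyroidism row has the second layout. A spanning cell is therefore likely, but the extracted text cannot confirm it.

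**Step 4: does section 5.6 split the grades?** Yes. Section 5.6.6.1 ties beta-blockers to Grade 2 hyperthyroidism, and section 5.6.6.2 ties corticosteroids to Grade 3-4. If the Table 3 cell spans the row, the table makes no such split.

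**Step 5: is there a precedence rule?** None was found. The pointer in section 5.2.1.1 sends the reader to section 5.6 for corticosteroid use, but does not say that section 5.6 overrides a row. The return reference in section 5.6.1 concerns dose modification.

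**Step 6: pneumonitis.** Both places direct corticosteroids, and both require a taper of at least 4 weeks (general instruction 3; section 5.6.2.1 for Grade 2). They differ only in whether prophylactic antibiotics depend on prolonged steroid use. The protocol does not define prolonged, so whether a taper of that length meets the condition is left to the reader.

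**The case against.** **The row may add to the general rule.** Table 3 as a whole does not exclude corticosteroids. Its general instructions call for them, section 5.2.1.1 refers to section 5.6 for their use, and the row is qualified by appropriateness. On this view the row lists an extra measure. This stands in part: it would be wrong to say that Table 3 simply replaces steroids with other drugs. But the table does not say that rows add to the general instructions. Elsewhere a row departs from them without comment: the hypothyroidism row covers Grades 2 to 4 and names only hormone replacement, and section 5.6.6.1 agrees with it. A reader therefore cannot assume that instruction 1 applies on top of every row.

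**The cell may belong to Grade 2 alone.** If so, the row gives no therapy for Grade 3-4, and the table and section 5.6.6 agree in substance. This cannot be ruled out from the text, though the layout of the other rows is against it.

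**Section 5.6 is guidance.** Its measures are offered as suggestions. That softens the conflict with section 5.6.6.2, but not the conflict between the row and the table's own instruction 1.

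**A stronger reading that the documents do not support.** A reader might infer that the conflict threatens the primary endpoint. A taper of at least 28 days fills much of the 42 days (plus or minus 3) allowed between the last pembrolizumab dose and surgery in section 6.2.10, so the resection CD3+ count could be taken under steroids on one reading and not on the other. That is possible for an individual patient, but it is speculative as a threat to the result:

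- The documents do not discuss the effect of steroids on the CD3+ count.
- Hyperthyroidism of any grade was 9/495 = 1.8% in the cited study (section 4.1.2). The documents give no Grade 3-4 share. Assuming 5% to 50%, the expected number among 40 patients is 40 × 0.0182 × 0.05 = 0.04 to 40 × 0.0182 × 0.50 = 0.36. Among the 26 evaluable patients assumed in section 7.2, the chance of at least one is 1 − (1 − 0.0182 × share)^26, or 0.02 to 0.21.
- Those figures count events at any time. Section 5.2.1.1 notes that immune events may appear months after the last dose, and those after surgery cannot touch the specimen. The cited study also enrolled patients with advanced disease, nearly all on 10 mg/kg or otherwise different schedules.
- Even if one of the 26 were certain not to respond, the power of the exact test (at least 8 responders, 40% true rate) would fall only from 0.878 to 0.846. Section 7.2 states 90% for the first of these; that difference has no bearing here.
- Table 3 directs steroids for many other events, so reconciling this row would leave the general question of steroid exposure before surgery as it was.

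**Conclusion.** The point holds as an inconsistency in patient-management instructions. For Grade 3-4 hyperthyroidism, section 5.6.6.2 and Table 3's general instructions 1 and 3 call for one treatment, the Table 3 row names another, and no passage settles which applies. It rests on one assumption, likely but unconfirmed: that the row's therapy cell spans Grades 2 to 4. The pneumonitis antibiotic mismatch is explicit in both texts and minor.

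The scope is two rows of one table. No design figure, test or sample size changes. Any effect on the CD3+ endpoint is speculative and would probably involve no patient or one, so it should not be given as the reason for the change. No view is taken here on which treatment is right.

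**What to change.** Reconcile the Table 3 hyperthyroidism row with general instruction 1 and section 5.6.6.2, and the Table 3 pneumonitis row with section 5.6.2.3, so that each event and grade carries one instruction. In doing so, make plain which grades the hyperthyroidism therapy entry covers. Add a sentence stating which text governs when a Table 3 row, the general instructions and section 5.6 differ. The clinical content is for the sponsor's clinicians to decide.

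The cost is protocol wording, carried in an amendment. No added data collection, sample-size change or analysis change is needed.

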#### 5.6.7 Hepatic:

5.6.7.1 For **Grade 2** events, monitor liver function tests more frequently until returned to baseline values (consider weekly).

5.6.7.1.1 Treat with IV or oral corticosteroids

5.6.7.2 For **Grade 3-4** events, treat with intravenous corticosteroids for 24 to 48 hours.

5.6.7.3 When symptoms improve to Grade 1 or less, a steroid taper should be started and continued over no less than 4 weeks.

#### 5.6.8 Renal Failure or Nephritis:

5.6.8.1 For **Grade 2** events, treat with corticosteroids.

- For **Grade 3-4** events, treat with systemic corticosteroids.
- When symptoms improve to Grade 1 or less, steroid taper should be started and continued over no less than 4 weeks.

5.6.9 **Management of Infusion Reactions:** Signs and symptoms usually develop during or shortly after drug infusion and generally resolve completely within 24 hours of completion of infusion.

Table 3 below shows treatment guidelines for subjects who experience an infusion reaction associated with administration of pembrolizumab (MK-3475).

**Table 3 Infusion Reaction Treatment Guidelines**

NCI CTCAE Grade	Treatment	ation at subsequent dosing
Grade 1  Mild reaction; infusion interruption not indicated; intervention not indicated	Increase monitoring of vital signs as medically indicated until the subject is deemed medically stable in the opinion of the investigator.	None
Grade 2  Requires infusion interruption but responds promptly to symptomatic treatment (e.g., antihistamines, NSAIDS, narcotics, IV fluids); prophylactic medications indicated for <=24 hrs	Stop Infusion and monitor symptoms. Additional appropriate medical therapy may include but is not limited to:  IV fluids Antihistamines NSAIDS  Acetaminophen Narcotics  Increase monitoring of vital signs as medically indicated until the subject is deemed medically stable in the opinion of the investigator.  If symptoms resolve within one hour of stopping drug infusion, the infusion may be restarted at 50% of the original infusion rate (e.g., from 100 mL/hr to 50 mL/hr). Otherwise dosing will be held until symptoms resolve and the subject should be premedicated for the next scheduled dose.  Subjects who develop Grade 2 toxicity despite adequate premedication should be permanently discontinued from further trial treatment administration.	Subject may be premedicated 1.5h (± 30 minutes) prior to infusion of pembrolizumab (MK-3475) with:  Diphenhydramine 50 mg po (or equivalent dose of antihistamine).  Acetaminophen 500-1000 mg po (or equivalent dose of antipyretic).
Grades 3 or 4	Stop Infusion.	No subsequent dosing
Grade 3:  Prolonged (i.e., not rapidly responsive to symptomatic medication and/or brief interruption of infusion); recurrence of symptoms following initial improvement; hospitalization indicated for other clinical sequelae (e.g., renal impairment, pulmonary infiltrates)  Grade 4:  Life-threatening; pressor or ventilatory support indicated	Additional appropriate medical therapy may include but is not limited to:  IV fluids Antihistamines NSAIDS  Acetaminophen Narcotics Oxygen   Pressors Corticosteroids Epinephrine  Increase monitoring of vital signs as medically indicated until the subject is deemed medically stable in the opinion of the investigator.  Hospitalization may be indicated.  Subject is permanently discontinued from further trial treatment administration.	
Appropriate resuscitation equipment should be available in the room and a physician readily available during the period of drug administration.		

